#### 9.2 DOCUMENTATION OF ADVERSE EVENTS

An AE or SAE occurring during the study must be documented in the subject's source documents and on the appropriate eCRF page. Information relating to the AE such as onset and cessation date and times, intensity, seriousness, relationship to study drug, and outcome is also to be documented in the eCRF (see Appendix 15.2 for definitions). Where possible, AEs should be recorded using standard medical terminology. The Investigator should attempt, if possible, to establish a diagnosis based on the presenting signs and symptoms. If several

signs or symptoms are clearly related to a medically-defined diagnosis or syndrome, the diagnosis or syndrome should be recorded on the eCRF page, not the individual signs and symptoms.

#### 9.3 FOLLOW UP OF ADVERSE EVENTS

All AEs should be followed until either resolution (or return to normal or baseline values), until they are judged by the Investigator to no longer be clinically significant, or for at least 30 days if the AE extends beyond the final visit. All SAEs that occur during the study will be followed until resolution, death, or the subject is lost to follow-up even if they are ongoing more than four weeks after completion of the final study visit. Supplemental measurements and/or evaluations may be necessary to investigate fully the nature and/or causality of an AE or SAE. This may include additional laboratory tests, diagnostic procedures, or consultation with other healthcare professionals. The eCRF pages should be updated with any new or additional information as appropriate.

If, at any time, the subject withdraws from the study and/or changes from study drug to commercially available Tyvaso, any AEs/SAEs that occur on Tyvaso (including product use errors, product quality problems, and therapeutic failures) will be reported following local post-marketing reporting requirements, or Continued Access Plan local reporting requirements (see Section 3.3.2.11). These events will not be included in the protocol analysis.

# 9.4 REPORTING RESPONSIBILITIES OF THE INVESTIGATOR All SAEs, regardless of expectedness or causality, must be reported to the Sponsor by fax/email ) within 24 hours of awareness.

A completed SAE Notification Report form along with any relevant hospital records and autopsy reports should be provided to Global Drug Safety at United Therapeutics Corporation. A follow-up SAE Notification Report form must be forwarded to Global Drug Safety at United Therapeutics Corporation within 24 hours of the receipt of any new or updated information. The Investigator must also promptly notify their Investigational Review Board (IRB) or Ethics Committee (EC) of the SAE, including any follow-up information, in accordance with applicable national regulations and guidelines set forth by the IRB or EC.

#### 9.5 PREGNANCY

If a study subject becomes pregnant during participation in this clinical study, site staff must notify the Sponsor within 24 hours of learning of the pregnancy by completing the Pregnancy

#### 9.6 SAFETY REPORTS

In accordance with national regulations, the sponsor will notify the appropriate regulatory authority(ies), and all participating Investigators of any AE that is considered to be possibly attributable to study drug and is both serious and unexpected. The Investigator must report these AEs to their IRB or EC in accordance with applicable national regulations and guidelines set forth by the IRB or EC.

#### 10 STATISTICAL CONSIDERATIONS

#### 10.1 DATA PROCESSING

The results of assessments will be transcribed into an eCRF for each subject who signs an ICF until study completion, or study discontinuation for any reason. A representative from the sponsor will verify eCRF data fields against source documentation. All data transmitted from the site will be reviewed and entered into a quality assured computerized database. Data clarifications will be generated and the database will be edited as appropriate. The eCRF screens are to be reviewed by the Investigator for completeness and accuracy. The Investigator must electronically sign each subject's eCRF to signify his/her approval of the data. The Investigator will be required to re-sign an eCRF if changes are made to a subject's eCRF by the site after the Investigator initially signs the eCRF. The database will be final when all outstanding queries have been resolved and all data management quality assurance procedures are complete.

#### 10.2 SAMPLE SIZE

No formal sample size calculation has been conducted. All eligible subjects from RIN-PH-201 may enter this study.

#### 10.3 ANALYSIS PLAN

All safety and efficacy data will be summarized in tables and listings and analyzed for trends over time. No formal hypothesis testing is planned.

The safety population will be defined as all subjects in the study that received inhaled treprostinil at any time during the course of the study. Safety analyses will be performed on the safety population. All AEs as recorded by the Investigators will be assigned MedDRA preferred terms by the sponsor for reporting purposes.

#### 10.4 INTERIM ANALYSES

Interim analyses for safety data will be performed at the request of the Data Monitoring Committee (DMC). Interim analyses for efficacy data are not planned for this study.

#### 10.5 OTHER ANALYSES

Exploratory analyses may be conducted based on available study data.

#### 10.6 DATA LISTINGS AND SUMMARIES

All data gathered in this study will be presented in summary tables and listings in the clinical study report.

#### 10.7 DATA MONITORING COMMITTEE

A DMC will be established for the study including physicians knowledgeable in the treatment of PH. Throughout the course of the study the DMC will meet on a regular basis to monitor the safety of the study. Meetings will occur as outlined in the DMC charter.

#### 11 PACKAGING AND FORMULATION

#### 11.1 CONTENTS OF STUDY DRUG

The Sponsor will supply study drug (treprostinil inhalation solution, 0.6 mg/mL), as clear liquid in 2.9 mL ampoules. The ampoules will be packaged in groups of four, sealed in aluminum pouches. There will be nine pouches per carton and each subject will receive three

cartons at Baseline, Week 12, and each scheduled follow-up visit thereafter (*i.e.*, every 12 weeks). Study drug will not be supplied at the Week 4 visit unless required for emergency purposes (*i.e.*, to replace lost study drug, etc.).

The Sponsor will supply commercially available TD-100 nebulizers (Tyvaso Inhalation System®) and accessories to the site in standard packaging labeled with the study number. The Tyvaso Inhalation will also be provided with the commercially available Instructions for Use (IFU).

Each subject will continue to use the assigned nebulizers provided in the RIN-PH-201 study for this study. In addition, the subjects will be provided with three months' worth of plastic accessories at Baseline, Week 12, and each scheduled follow-up visit thereafter. Nebulizers will be replaced at least every two years (date determined based off of first use in RIN-PH-201).

#### 11.2 LABELING

The foil pouch and the outer carton will each be labeled with the same information and sent to the site. At a minimum, the study medication outer packaging (pouch and carton) will be labeled to disclose clearly the product name, study number, kit identification number, expiry date, Sponsor's name and address, instructions for use, and storage information (subject to regulatory requirements in each study region or country).

Study subjects will receive commercially available TD-100 nebulizers and accessories separately from study drug. Study subjects will utilize the TD-100 nebulizers from the RIN-PH-201 study at study entry. Subjects will receive replacement parts every three months as part of device resupply kit. The nebulizers and accessories will be supplied using standard packaging labeled with the study number.

#### 11.3 STORAGE AND HANDLING OF CLINICAL TRIAL MATERIAL (CTM)

All study drug will be stored at room temperature  $25^{\circ}$ C (77°F) with excursions permitted to  $15^{\circ}$ C- $30^{\circ}$ C ( $59^{\circ}$ F –  $86^{\circ}$ F). Study drug should not be frozen, refrigerated, or exposed to heat. Keep the ampoules in the foil pouch to protect from light. Once the foil pouch is opened, use

within seven days. See investigational medicinal product label for information on use and storage of the product.

Study drug will be stored in a securely locked cabinet or enclosure with appropriate temperature monitoring. Access should be strictly limited to the Investigators and their designees. Neither the Investigators nor any designees may provide study drug to any subject not participating in this protocol.

#### 11.4 SUPPLY AND RETURN OF CTM

Study sites will be supplied with a sufficient quantity of study drug to begin enrollment in the study. At Baseline, an IXRS will be utilized to assign study drug for the first 12-week treatment interval. At subsequent study visits, the IXRS will be utilized by study staff to assign subsequent study drug kits to the subjects. Starting at Week 12 and at every scheduled study visit thereafter, all study drug dispensed to a subject should be returned to the study site, including all used and unused ampoules. Subjects may also return used ampoules at the Week 4 visit; however, unused ampules should not be returned until the Week 12 visit to ensure the subject has enough drug to get through Week 12.

At the end of the study, nebulizers used during the study should be collected from each subject.

#### 11.5 DRUG ACCOUNTABILITY

The Investigator is responsible for study drug accountability and reconciliation overall and on a per subject basis. Drug accountability records are to be maintained during the study and these records include, but are not limited to: the amount of study drug received from the sponsor, the amount dispensed to each subject, and the amount of used/unused study drug returned to the site from the subject.

At each visit, site personnel will:

- Collect and document all study drug returned by the subject (both used and unused [unused drug will not be collected at the Week 4 visit to ensure the subject has enough drug to get through the Week 12 visit]).
- Compute study drug compliance using the dosing instructions given to the subject since the previous study visit and the amount of study drug returned.

- Re-educate the subject about the importance of following the prescribed dosing regimen (if compliance is low).
- Review the subject dosing diary, if applicable (the use of a dosing diary is optional for this open-label study)

Once a representative from the Sponsor is able to confirm drug accountability for a completed subject, unused study drug and nebulizers will be returned to a Sponsor designated location for destruction.

#### 12 REGULATORY AND ETHICAL OBLIGATION

#### 12.1 APPLICABLE REGULATORY REQUIREMENTS

The study will be conducted in accordance with ICH and GCP guidelines and all applicable national regulations. The Sponsor will obtain the required approval from each national regulatory authority to conduct the study. During the conduct of the study, an annual safety report will be compiled by the sponsor for submission to those regulatory authorities and IRBs/ECs that require it. Any additional national reporting requirements as specified by the applicable regulations, regulatory authorities, or IRB/EC will also be fulfilled during the conduct of the study.

#### 12.2 INFORMED CONSENT REQUIREMENTS

Before a subject is enrolled in the study, the Investigator or his/her designees must explain the purpose and nature of the study, including potential benefits and risks and all study procedures to the subject. The subject must sign and date an IRB/EC-approved informed consent form prior to the conduct of any study-related activities. A copy of the signed consent form will be given to the subject and the original will be retained in the study site's records.

#### 12.3 INDEPENDENT ETHICS COMMITTEE/INSTITUTIONAL REVIEW BOARD

Prior to study initiation at each site, the Investigator will obtain approval for the study from an appropriate IRB/EC and provide the sponsor with a copy of the approval letter. The IRB/EC must also review and approve the study site's informed consent form and any other written information provided to the subject prior to enrollment, as well as any advertising materials used for subject recruitment. Copies of the informed consent form and advertising materials

must be forwarded to the Sponsor for review before submission to the IRB/EC prior to the start of the study.

If, during the study, it is necessary to amend either the protocol or the informed consent form, the Investigator is responsible for obtaining IRB/EC approval of these amended documents prior to implementation. Copies of the IRB/EC correspondence and approval letters must be sent to the Sponsor.

During the conduct of the study, an annual progress report will be compiled by the Sponsor for submission to those IRBs/ECs that require it.

A written summary of the study will be provided by the Investigator to the IRB/EC following study completion or termination according to the IRB or EC standard procedures. Additional updates will also be provided in accordance with the IRB/EC's standard procedures.

#### 12.4 PRESTUDY DOCUMENTATION REQUIREMENTS

Before the commencement of the clinical trial, at a minimum, the following documents will be provided to the site: Investigators' Brochure, Protocol, Informed Consent Form, Dosing Diary, the Tyvaso Inhalation System IFU, Budget Agreement, and Case Report Form.

At a minimum, the site will be required to provide the following documents to United Therapeutics Corporation or designee prior to study start: Signature page of the protocol, Form FDA 1572, Financial Disclosure Form, IRB/EC Composition and Roster, IRB/EC protocol and informed consent approval letters, and Curriculum Vitae of study staff listed on the 1572.

#### 12.5 SUBJECT CONFIDENTIALITY

Every effort will be made to keep medical information confidential. United Therapeutics Corporation, the FDA or other regulatory bodies, and the IRB/EC governing this study may inspect the medical records of any subject involved in this study. The Investigator may release the subject's medical records to employees or agents of the Sponsor, the IRB/EC or the FDA or appropriate local regulatory agencies for purposes of checking the accuracy of the

data. A number will be assigned to all subjects and any report published will not identify the subject's name.

#### 13 ADMINISTRATIVE AND LEGAL OBLIGATIONS

#### 13.1 PROTOCOL AMENDMENTS AND STUDY TERMINATION

Protocol amendments that could potentially adversely affect the safety of participating subjects or that alter the scope of the investigation, the scientific quality of the study, the experimental design, dosages, duration of therapy, assessment variables, the number of subjects treated, or subject selection criteria may be made only after consultation between United Therapeutics Corporation or its designee and the Investigator.

All protocol amendments must be submitted to and approved by the appropriate regulatory authorities and IRB/EC prior to implementation.

A report documenting study termination must also be submitted to and acknowledged by the appropriate IRB/EC for each study site.

At the end of the study, where applicable, a final report will be provided to the local regulatory agencies.

#### 13.2 STUDY DOCUMENTATION AND STORAGE

In accordance with federal/national regulations, ICH, and GCP guidelines, the Investigator must retain study records for at least two years after the last approval of a marketing application in an ICH region and until there are no pending or contemplated marketing applications in an ICH region or at least two years have elapsed since the formal discontinuation of clinical development of the investigational product. The Investigator must notify United Therapeutics Corporation before any disposal or change in location of study records.

#### 13.3 STUDY MONITORING AND DATA COLLECTION

In accordance with federal/national regulations, ICH, and GCP guidelines, monitors for United Therapeutics Corporation or its designee will periodically contact the site and conduct on-site visits. During these visits, the monitor will at a minimum: confirm ethical treatment of subjects, assess study progress, review data collected, conduct source document

verification, verify drug accountability periodically, and identify any issues requiring resolution.

The Investigator agrees to allow the monitor direct access to all relevant documents and to allocate his/her time and his/her staff to the monitor to discuss any findings or any relevant issues.

#### 15 APPENDICES

#### 15.1 PROCEDURE FOR SIX-MINUTE WALK TEST

#### General Procedures

The 6MWT should be administered by the same tester at each study site throughout the study, whenever possible. The administration of the test and specifications of the testing area should be generally consistent with the American Thoracic Society guidelines and the usual practice of the investigative site.

The area used for the 6MWT should be pre-measured at approximately 30 meters in length and at least 2 to 3 meters in width. There should be no turns or significant curves to the 6MWT area. The length should be marked with gradations to ensure the accurate measurement of the distance walked. The area should be well ventilated. The tester may be at the starting end of the corridor or at the midpoint of the corridor with a stop-watch. Intermittent rest periods are allowed if the subject can no longer continue. If the subject needs to rest briefly, he/she may stand or sit and then begin again when he/she is sufficiently rested but the clock will continue to run. At the end of 6 minutes, the tester will call "stop where you are" while simultaneously stopping the watch and then measure the distance walked.

#### Instructions to the Subject

Subjects will be instructed that the preceding meal should be light. Subjects should be told to wear comfortable clothing and sneakers or comfortable walking shoes. The person administering the test will use the following **exact** dialogue with the subject:

"The purpose of this test is to find out how far you can walk in 6 minutes. You will start from this point and follow the hallway to the marker (e.g., chair) at the end, turn around and walk back. When you arrive back at the starting point you will go back and forth again. You will go back and forth as many times as you can in the 6-minute period. You may stop and rest if you need to. Just remain where you are until you can go on again. However, the most important thing about the test is that you cover as much ground as you possibly can during the six-minutes. I will tell you the time, and I will let you know when the 6 minutes are up. When I say STOP, please stand right where you are."

After these instructions are given to the subject, the person administering the test will then ask:

"Do you have any questions about the test?"

The person administering the test will then start the test by saying the following to the subject:

```
"Are you ready?"
"Start when I say "GO."
```

The person administering the test will tell the subject the time at each minute by saying:

```
"You have 5 minutes to go."
"You have 4 minutes to go."
"You have 3 minutes to go."
```

"You have 2 minutes to go."

"You have 1 minute to go."

At 6 minutes, the person administering the test will tell the subject: "stop where you are."

No other instruction or encouragement will be given during the test. Eye contact with the subject should be avoided during the test.

<sup>1 ATS Statement: Guidelines for the Six-Minute Walk Test. Am J Respir Crit Care Med 2002; 166: 111–117.

<sup>2 Holland, A. E., M. A. Spruit, T. Troosters, M. A. Puhan, V. Pepin, D. Saey, M. C. McCormack, B. W. Carlin, F. C. Sciurba, F. Pitta, J. Wanger, N. MacIntyre, D. A. Kaminsky, B. H. Culver, S. M. Revill, N. A. Hernandes, V. Andrianopoulos, C. A. Camillo, K. E. Mitchell, A. L. Lee, C. J. Hill and S. J. Singh (2014). "An official European Respiratory Society/American Thoracic Society technical standard: field walking tests in chronic respiratory disease." Eur Respir J 44(6): 1428-1446.

#### 15.2 GUIDELINES AND DEFINITIONS FOR RECORDING ADVERSE EVENTS

The Investigator or a designated member of his/her staff will probe each subject for any AEs that may have occurred. The Investigator should always ask the same question when conducting the verbal probe in order to ensure uniformity between subjects. The Investigator should ask:

"How are you doing (feeling)?"

Based on the subject's response to this question, the Investigator should ask additional questions relevant to the specific complaint such as:

"How severe is/was the symptom?"

"How often did the symptom occur?"

"How long did the symptom last?"

It is the Investigator's responsibility to review the results of all diagnostic and laboratory tests as they become available and ascertain if there is a clinically significant change from Baseline. If the results are determined to be a clinically significant change from Baseline, this should be reported as an AE. The Investigator may repeat the diagnostic procedure or laboratory test or request additional tests to verify the results of the original tests. When possible, a diagnosis associated with the abnormality should be used as the reported AE.

Using provided definitions, the Investigator will then:

(1) rate the intensity and seriousness of the AE, (2) estimate the causality of the AE to study drug, and (3) note actions taken to counteract the AE.

Definitions of Intensity, Seriousness, Causality, Action Taken, and Outcome

#### **INTENSITY**

An assessment of the relative intensity (severity) of an AE is based on the Investigator's clinical judgment. The maximum intensity encountered during the evaluation period should be checked. The assessment of intensity should be independent of the assessment of the seriousness of the AE.

#### **SERIOUSNESS**

A serious AE is one that represents an actual or potential significant hazard. This includes, but is not limited to, an event that is fatal, life-threatening, permanently or severely disabling, requires or prolongs inpatient hospitalization\*, is a congenital abnormality (offspring of subject) or is medically significant (important medical events that may not result in death, be life-threatening, or require hospitalization may be considered an SAE when, based upon appropriate medical judgment, they may jeopardize the subject and may require medical or surgical intervention to prevent one of the outcomes listed in this definition).

\*Hospitalizations that would not be considered SAEs include those for:

- Routine treatment or monitoring of the study indication not associated with any deterioration in condition (e.g., hospitalization for a routine RHC).
- Treatment which was elective or pre-planned, for a pre-existing condition not associated with any deterioration in condition (e.g., pre-planned operation which does not lead to further complications etc.).
- Treatment of an emergency, in an outpatient setting for an event not fulfilling any of the definitions of serious as given above and not resulting in hospital admission.

#### **CAUSALITY**

An estimate of causality between a specified AE and the study drug is made by the Investigator. Several factors should be considered when determining causality. These factors include temporal relationship and response to withdrawal or reintroduction of the study drug.

Definitions of the causality categories are as follows:

- NOT RELATED There is not a temporal relationship to study drug administration (too early, or late, or study drug not taken), or there is a reasonable causal relationship between another drug, or concurrent disease and the SAE, or any of the following:
  - An event that precedes the first administration of study drug
  - An event for which the cause is clearly related to an external event
  - Temporal relationship to study drug is atypical
  - Is readily explained by an intercurrent illness AND has an expected level of severity, duration and resolution
  - An alternative explanation (concomitant drug, intercurrent illness) is likely
- POSSIBLE There is a reasonable causal relationship between the study drug and the SAE. Dechallenge information is lacking or unclear, study drug administration was not modified in response to the SAE, or any of the following:

- Has a reasonable temporal relationship to study drug
- The event has a plausible biological link to the activity of the study drug
- Is unlikely to be related to an intercurrent illness or has an unexpected degree of severity, duration or complication
- PROBABLE There is a reasonable causal relationship between the study drug and the SAE. The event responds to dechallenge the event resolves or improves with modification of study drug administration. Rechallenge (the original study drug was restarted) is not required, or any of the following:
  - Has a reasonable temporal relationship to study drug
  - The event has a plausible biologic link to the activity of the study drug
  - Not readily explained by an intercurrent illness
  - Not readily explained by external event
  - Improves on discontinuation of study drug
  - If study drug has been discontinued, may recur or reintroduction of study drug

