11 SAFETY ANALYSES

11.1 ADVERSE EVENTS

AEs are captured from the time the Informed Consent Form is signed. Any AEs that are ongoing at the Study Termination Visit from study RIN-PH-201 are recorded as continuing AEs in the RIN-PH-202 study. All AEs with an onset date on or after the first dose of inhaled treprostinil in the RIN-PH-202 study or AEs ongoing from the parent study will be included in data listings and summaries.

The AEs will be coded using the Medical Dictionary for Regulatory Activities (MedDRA), and all summaries will utilize the Preferred Term (PT) and/or System Organ Class (SOC) to categorize AEs. All AEs will be organized by treatment group in the parent study and listed by subject, including onset date (day), cessation date (day), verbatim term, corresponding

SOC and PT, seriousness, date AE became serious, severity, frequency, relationship to study drug, action taken with study drug, and outcome.

The overall summary of AEs includes the number of subjects with any AE, the number of subjects with any study drug-related AEs, the number of subjects with AEs leading to study drug withdrawal, the number of subjects with AEs leading to death, the number of subjects with any serious AEs, and the number of subjects with any study drug-related serious AEs.

The summaries of AEs by SOC and PT will be provided by parent study treatment group and overall. The summaries of AEs, serious AEs, non-serious AEs, AEs probably or possibly related to inhaled treprostinil, and AEs leading to permanent discontinuation of inhaled treprostinil will include the number of subjects (percent of subjects) and number of events for each reported PT.

The total number of AEs and the AE rates will be calculated and summarized for each display, as appropriate. The AE rate will be calculated as the total number of AEs divided by the total patient years of exposure to study drug per treatment group in the parent study.

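### Protocol 15.2 allows an event with a reasonable study-drug relationship to be rated Not Related, and gives no rule for choosing between overlapping causality categories

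*Protocol*

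**What the plan says.** Protocol 15.2 has the investigator estimate causality for each AE, using the definitions it provides. The rating is recorded in the eCRF (Protocol 9.2).

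- **Not Related** is met when there is no temporal relationship, "or there is a reasonable causal relationship between another drug, or concurrent disease and the SAE, or any of the following". The bullets that follow include "An alternative explanation (concomitant drug, intercurrent illness) is likely" and "An event that precedes the first administration of study drug".
- **Possible** opens with "There is a reasonable causal relationship between the study drug and the SAE" and continues: "Dechallenge information is lacking or unclear, study drug administration was not modified in response to the SAE, or any of the following".
- **Probable** opens with the same sentence, adds a response to dechallenge, and ends: "Rechallenge (the original study drug was restarted) is not required, or any of the following".

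The lists under Possible and Probable share two items: reasonable timing and a plausible biologic link. Nothing says which category applies when more than one fits.

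SAP 11.1 counts subjects with drug-related AEs and with drug-related serious AEs, and summarises "AEs probably or possibly related to inhaled treprostinil" as one pooled group (Table 14.3.1.7). Protocol 9.6 concerns sponsor notification of "any AE that is considered to be possibly attributable to study drug and is both serious and unexpected".

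**The concern.** A usable causality scale gives one answer for one set of facts. This one does not, and the gap lies on the boundary that the tables use. Not Related is defined by the presence of another cause, whereas Possible and Probable are defined by the presence of a drug cause. Both can be present in the same event. The indication is pulmonary hypertension with interstitial lung disease, so every subject carries a concurrent disease that can explain cough, dyspnoea, infection or respiratory deterioration.

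The study has no control group, and the clinical hypothesis in Protocol 1.4 concerns long-term safety. Attribution of events to the drug therefore leans on the investigator's rating. With approximately 100 centers, a definition that permits opposite answers can add variation between investigators to the drug-related counts.

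**Working it through.** The plan states no figure here, so the check is one of logic.

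**One event against the three definitions.** Take a respiratory AE with reasonable timing, a plausible biologic link, and study drug left unmodified. The investigator judges the drug a reasonable cause and the underlying lung disease also a reasonable and likely cause.

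| Category | Condition in the text | Met? |
|---|---|---|
| Not Related | Concurrent disease reasonably causal, or alternative explanation likely | Yes, by either |
| Possible | Drug reasonably causal, and study drug not modified | Yes |
| Probable | Drug reasonably causal, and one listed item such as timing | Yes, if the list is a true alternative to dechallenge |

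If the lists under Possible and Probable are ignored, Probable drops out because there is no positive dechallenge. Not Related and Possible are both still met. Removing the list under Not Related as well does not help, because the competing-disease condition stands in its opening text.

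**Enumeration.** The criteria were coded as conditions and every internally consistent combination was listed. The consistency rules were: unmodified drug means dechallenge is lacking; ready explanation by intercurrent illness means an alternative is likely and excludes the item saying intercurrent illness is unlikely; a drug cause requires reasonable timing.

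- Timing and drug cause: 5 combinations.
- Other cause, external cause, expected course, biologic link: 2 × 2 × 2 × 2 = 16.
- Intercurrent illness and alternative explanation: 5.
- Drug modification and dechallenge: 4.
- Total: 5 × 16 × 5 × 4 = 1,600 profiles, of which 1 × 16 × 5 × 4 = 320 have a reasonable drug cause.

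Not Related keeps its full text in all four readings below.

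| Reading of Possible and Probable | All three met | Not Related plus Possible or Probable | Possible and Probable |
|---|---|---|---|
| Everything joined by or | 1,434 | 1,434 + 66 + 30 = 1,530 | 1,498 |
| Opening sentence required, plus any one item | 288 | 288 | 320 |
| Lists ignored | 0 | 144 + 72 = 216 | 0 |
| All items required | 0 | 50 + 12 = 62 | 0 |

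These are counts of logical combinations, not estimates of how often events overlap. They show two things. The Possible/Probable overlap disappears on a strict reading, while the overlap with Not Related does not.

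**Effect of the change.** If Not Related also requires no reasonable drug relationship, it cannot coincide with a category that requires one, so 288, 216 and 62 each become 0. In the first reading Possible can be met by timing alone, so overlap would remain. The opening sentence must therefore be made a required condition as well. Deleting the open lists alone would leave the 216.

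**The case against.** Causality is described as an estimate for which several factors are weighed, so the lists can be taken as guidance to judgment and not as an algorithm. That is a fair account of practice. But 15.2 presents them as the definitions the investigator is to use, and judgment cannot settle a case in which both the drug and the disease are reasonable causes and the text names no winner.

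Several stronger inferences are tempting, and the documents do not support them.

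- *The drug-related tables are not reproducible.* They are: the rating is in the eCRF and the SAP counts what was recorded. What is not assured is that investigators would rate alike.
- *Timing alone makes an event Possible or Probable.* This holds only if the opening sentence is optional. Possible and Probable each begin with a full sentence requiring a reasonable drug relationship, and on that reading timing alone satisfies neither.
- *Possible/Probable overlap distorts the results.* Table 14.3.1.7 pools the two, and no table separates them.
- *A cough that began on blinded treprostinil is Not Related by rule, because it precedes first dosing in this study.* The protocol does not define study drug for this purpose. Its Day 1 footnote belongs to Table 6-1, while inclusion criterion 2b and the Baseline walk test in 7.1 use the same term for parent-study drug. Nothing says that carried-over AEs are re-rated. The wording is unclear, but the fault is not established. The 54% cough figure from TRIUMPH-I is any reported cough over 12 weeks in a different population, so it does not bound carry-over here.
- *Serious events may not reach the sponsor.* Protocol 9.4 sends all SAEs within 24 hours whatever the causality, and 9.6 does not make the 15.2 category decisive.

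It also stands that all AEs, SAEs, deaths, cardiopulmonary hospitalizations and exacerbations are summarised irrespective of causality, that a DMC reviews safety, and that no hypothesis is tested.

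**Conclusion.** The point holds for the boundary between Not Related and the two related categories. An event with a reasonable study-drug relationship can be placed in Not Related under the stated text whenever another drug or the lung disease is also a reasonable or likely cause, and no rule decides between them. This survives every reading of the Possible and Probable lists that was tried.

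The consequence is possible inconsistency between investigators in the drug-related AE and SAE counts and in Table 14.3.1.7, mainly for respiratory events. The documents contain no data on rating disagreement, so the size cannot be estimated. A reader might infer that the related share could lie anywhere from 0% to 100%, but nothing in the documents turns that logical possibility into an expected range.

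The statement that only this boundary matters assumes that drug-related in the overall AE summary means Possible or Probable. The SAP does not say so explicitly for that summary. Because the descriptive counts are themselves the safety result of an uncontrolled extension, the wording should be corrected, although no formal inference depends on it.

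**What to change.** In Protocol 15.2:

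1. Require for Not Related that there is no reasonable causal relationship with study drug. State that an event with both a reasonable drug relationship and an alternative explanation is rated at least Possible.
2. Make the opening sentence of Possible and Probable a required condition. Reserve Probable for events that also improve on dechallenge or are not readily explained otherwise; other events meeting the opening sentence are Possible.
3. State whether the first administration of study drug includes blinded study drug in RIN-PH-201 for AEs carried over into this study. Naming blinded study drug, and not treprostinil, avoids any dependence on the parent-study assignment.
4. Replace SAE with AE/SAE in the category definitions, since every AE is rated.

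The cost is one reworded appendix page and a note to sites, with no new data. Somewhat more events will be rated Possible. If RIN-PH-201 used the same text, the two studies would then follow slightly different rules, and this should be noted wherever drug-related counts are compared with the parent study.
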